We require a minimum of 342 DMPA clients randomized to receive care from either the LHV or an LHW (1:1 allocation) for 90% power and 5% significance level to test the non-inferiority hypothesis that LHWs can screen potential DMPA clients for method initiation just as adequately as LHVs with a non-inferiority margin of 7.5%, assuming that both LHVs and LHWs perform at a 95% success rate. In Pakistan, there is usually at least one LHV assigned to a health facility and many more LHWs affiliated with and under the supervision of resident LHVs. Therefore, we will use a 3 to 1 ratio of LHWs to LHVs at each health facility in the trial.

For logistical reasons, we plan to obtain the full target sample size of 342 DMPA initiators from the 5 urban health facilities in Karachi to ensure that adequate analyses can be done with this group. We will recruit additional participants (~100) from 5 rural facilities in Thatta to help assess possible differences in performance between LHV and LHWs in rural and urban areas, but the expectation is that there will be no difference. LHWs undergo standardized training in Pakistan. If we can be comfortable that providers in rural and urban areas perform in similar manner, the overall sample size for the analysis may be pooled for an increase in power. The decision whether to pool the data or not will be made during the blind review of the data as described below.

Given the relationship between LHWs and LHV within clinics, we plan to account for the correlations of participant outcomes within providers and providers within clinics in the analysis. We expect that some of these correlations would lead to decreases in power and others to lead to increases in power for within clinic comparisons. Power calculations were not adjusted for these potential correlations as the net effect on power may be offset with each other.

V. General Analytic Considerations

A. Data Sources

A.1 Client exit interview

Client exit interviews measure the study's secondary outcomes of client satisfaction with the method and provider. The exit interview also provides additional information related to appropriate screening such as discussion of side effects, warning/danger signs, advantages and disadvantages of DMPA use with clients. The client exit interview includes questions on the following domains:

1. Sociodemographic characteristics
2. Experiences using contraceptive methods
3. Factors in her decision to use DMPA

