Even though the study is open labeled, the randomization was prepared by an independent randomization manager and data management is separated from the analysis team. Thus, the analysis team will initially be blinded to the group assignments. Unblinding of the analysis team will follow a three-step process: First, key decisions regarding the primary and secondary outcomes listed above will

be made blinded to study group assignment. These outcome variables will be constructed, checked for missing data, distributional anomalies or other problems, finalized and verified. Decisions about re-categorization, transformation, missing data, and final variable definition will be completed after initial descriptive analysis and prior to further analysis for the specific objectives. Descriptive analysis of the outcomes will be done by facility and rural/urban designation. This check will also include a check of protocol violations, such as randomization errors (this review will be coordinated between the data manager and the randomization manager to maintain blinding of the analysis team) to decide if any data should be excluded from the analysis. Primary analysis will be conducted based on the intent to treat (ITT) approach where all participants randomized will be analyzed in the study group to which they were randomized. During blind review, decisions will be made regarding any modification to the ITT principle for primary analysis and whether a per protocol analysis will be conducted as secondary or sensitivity analysis. Second, once these key decisions have been made, the randomization manager will provide a participant list with blinded study arm assignments to the analysis team. A descriptive bivariate analysis will be done using blinded treatment assignments stratified by rural/urban designation to assess whether pooling the data will be appropriate. A decision whether further analysis will be pooled or not will be done at this time. Partial blinding will be maintained until statistical conclusions regarding the primary outcome (screening outcome) and primary analysis have been made and verified. This will be based on the pooled data or on the urban data only depending on the decision made in the prior step. The analysis team will be fully unblinded for all remaining analysis.

E. Test Size and Confidence Levels

The type I error for the non-inferiority test and other performance outcomes will be set at the two-sided $\alpha=0.05$ significance level.

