VI. Analysis of Fieldwork Data

An analysis of fieldwork data will be presented. This will include the number of DMPA acceptors approached, included, and randomized to LHW or LHV care.

VII. Analysis of participant characteristics

A descriptive summary of DMPA user, LHV, and LHW characteristics will be presented by urban and rural setting. DMPA client characteristics will include age, marital status, education, number of children, desire for more children, and birth spacing plans. Provider characteristics will include age, marital status, education, years of service, and years of DMPA experience.

VIII. Analysis of Study Objectives

We plan to compare a series of indicators of the performance of LHWs compared to LHVs in the provision of injectable contraception services. Our primary outcome, appropriate screening, is a binary variable comprised of the gold standard nurse's assessment of client eligibility for DMPA compared with the LHV's or LHW's assessment of client eligibility. If the LHV's or LHW's assessment agrees with the gold standard nurse's assessment, the screening is deemed appropriate.

Analytical model

We will test the non-inferiority hypothesis that LHWs can screen potential DMPA clients for method initiation just as adequately as LHV with a non-inferiority margin of 7.5%. Given the relationship between LHWs and LHV within clinics, we will employ a generalized mixed model using a logit link to account for the correlations of participant outcomes within providers and providers within clinics. Random effects will be included for clinics and providers within clinic. The non-inferiority test will be conducted at a 5% significance level. A similar approach will be used to compare appropriate counseling. No covariate adjustments are planned for the primary analyses. However, exploratory analyses will include the following covariates: LHV/LHW age, marital status, education level, years of service, years of experience with DMPA, and average DMPA-IM injections given per month prior to the trial. Years of service, years of experience with DMPA, and average injections per month will be analyzed either as categorical or continuous variables based on exploratory analyses; either odds ratios or beta coefficients will be reported.

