Use of client (re)injection log*	Descriptive	urban/rural	LHW/LHV questionnaire, qLHW6
Objective 2 Outcomes			
Client satisfaction with DMPA*	Descriptive	Cadre, DMPA type	Client exit interview, q313
Client satisfaction with service delivery*	Descriptive	Cadre, DMPA type	Client exit interview, q318
Client comfort asking provider questions*	Descriptive	Cadre, DMPA type	Client exit interview, q303
Friendly and respectful behavior by provider*	Descriptive	Cadre, DMPA type	Client exit interview, q301

* If the data are pooled, there will be no urban/rural stratification

Objective 1 Table Shells: Screening and counseling for DMPA

Table 1: Odds of appropriate screening and counseling for DMPA initiation by Lady Health Workers compared with Lady Health Visitors in Pakistan

OR	90%CI	p-value
Appropriate screening		
Appropriate counseling		

Appropriate screening defined as agreement between the provider and independent assessment by a gold standard nurse
Appropriate counseling defined as having discussed side effects, warning/danger signs, advantages, and disadvantages of DMPA

95% CI and p-value reported for test of non-inferiority

Table 2: Exploratory analysis of factors affecting appropriate screening for DMPA initiation by Lady Health Workers compared with Lady Health Visitors in Pakistan

	N (%)	OR (or β)	95%CI	p-value
Age				
Age cat 1				
Age cat 2				
Etc.				
Marital status				
Marital status 1				
Marital status 2				
Etc.				
Education level				
Education level 1				
Education level 2				
Etc.				
Years of service				
Categorical or continuous TBD				
Years of DMPA experience				
Categorical or continuous TBD				
Avg. DMPA injections/month				
Categorical or continuous TBD				

Appropriate screening defined as agreement between the provider and independent assessment by a gold standard nurse

Table 3: Exploratory analysis of factors affecting appropriate counseling for DMPA initiation by Lady Health Workers compared with Lady Health Visitors in Pakistan

	N (%)	OR (or β)	95%CI	p-value
Age				
Age cat 1				
Age cat 2				
Etc.				
Marital status				
Marital status 1				
Marital status 2				
Etc.				
Education level				
Education level 1				
Education level 2				
Etc.				
Years of service				
Categorical or continuous TBD				
Years of DMPA experience				
Categorical or continuous TBD				
Avg. DMPA injections/month				
Categorical or continuous TBD				

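### The SAP gives the primary non-inferiority test two different levels (two-sided 0.05 with a 95% CI, and a 90% CI), and 342 clients at 90% power is reproduced only at one-sided 5%

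*SAP*

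**What the plan says.** Five places in the SAP bear on the level of the primary test.

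- **V.E, Test Size and Confidence Levels:** "The type I error for the non-inferiority test and other performance outcomes will be set at the two-sided" 0.05 level.
- **Objective 1 Table Shells, Table 1, column header:** the interval for the odds ratio of appropriate screening and of appropriate counseling is labelled 90% CI.
- **Same table, footnote:** "95% CI and p-value reported for test of non-inferiority".
- **IV, Sampling Design:** 342 clients, allocated 1:1, "for 90% power and 5% significance level to test the non-inferiority hypothesis", "with a non-inferiority margin of 7.5"%, and "assuming that both LHVs and LHWs perform at a 95% success rate".
- **VIII, Analytical model:** "The non-inferiority test will be conducted at a 5% significance level".

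The Protocol (Sample size; Data analysis) repeats the 5% level, also without sidedness. On clustering, SAP IV says: "Power calculations were not adjusted for these potential correlations as the net effect on power may be offset with each other".

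**The concern.** A non-inferiority claim looks in one direction only: whether LHWs are worse than LHVs by more than the margin. A two-sided 0.05 rule therefore allows a false claim 2.5% of the time and is read from the lower limit of a 95% interval. A 90% interval allows 5%. V.E and the footnote point to the first rule and the table header points to the second. The statements that give a bare 5% fit either.

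A result whose lower limit clears the margin on the 90% interval can miss it on the 95% interval. According to the Protocol's Introduction, the trial is meant to support a change in national policy and in a WHO recommendation, so its main decision rule should not be open to choice once results are known. The blind data review in SAP V.D does not close the gap. It covers variable definitions, missing data, exclusions, departures from intention to treat, and pooling, but not the test level.

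The second question is which level the sample size was built on, because that decides whether the stated 90% power goes with the rule in V.E.

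**Working it through.** **Inputs (SAP IV).** Success rate 0.95 in both arms; margin 0.075, taken as an absolute difference; 1:1 allocation; power 90%; total 342, so 171 per arm. The documents name no formula, so three common ones were tried. Normal quantiles: 1.645 (one-sided 0.05), 1.960 (one-sided 0.025), 1.282 (90% power). Variance under the alternative: 2 × 0.95 × 0.05 = 0.095.

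**1. Unpooled Wald.** n per arm = (z_α + z_β)² × 0.095 / 0.075².
- One-sided 0.05: 144.6, so 145 per arm, 290 in total.
- One-sided 0.025: 177.5, so 178 per arm, 356 in total.

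**2. Wald with continuity correction.** n_c = (n/4) × [1 + √(1 + 4/(n × 0.075))]², with the unrounded n from step 1.
- One-sided 0.05: 170.3, so 171 per arm, **342** in total.
- One-sided 0.025: 203.3, so 204 per arm, 408 in total.

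**3. Farrington-Manning score.** The restricted null rates are 0.893 (LHW) and 0.968 (LHV), with null variance 0.8933 × 0.1067 + 0.9683 × 0.0317 = 0.126. n = (z_α√0.126 + z_β√0.095)² / 0.075².
- One-sided 0.05: 170.4, so 171 per arm, **342** in total.
- One-sided 0.025: 211.6, so 212 per arm, 424 in total.

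The plan's own figure is thus reproduced exactly, by two methods, at one-sided 5%. At one-sided 2.5% none of the three gives it.

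**4. Power for the planned numbers (normal approximation, no clustering).**

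| Method | 342, one-sided 0.05 | 342, one-sided 0.025 | 442 pooled, one-sided 0.025 |
|---|---|---|---|
| Farrington-Manning | 90.1% | 82.2% | 91.3% |
| Continuity-corrected | 90.1% | 83.5% | 92.5% |
| Unpooled Wald | 93.8% | 88.9% | 95.1% |

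**5. Can the choice reverse the verdict?** As an illustration, assume simple unclustered Wald intervals, 171 per arm, and LHVs correct in 162/171 (94.7%).
- LHWs correct in 158/171: difference −2.34 points, standard error 2.65 points. Lower limit −6.7 on the 90% interval (non-inferior) and −7.53 on the 95% interval (not shown).
- LHWs correct in 157/171: lower limits −7.4 and −8.2, again a split verdict.

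Both results lie close to the rates the plan assumes.

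**The case against.** The best defence is that V.E is the section written to fix the test size, that it does so explicitly, and that the footnote agrees with it. The bare 5% statements are silent on sidedness rather than contradictory, and Tables 2 and 3 use 95% intervals. On this reading one column header in an empty shell is a slip, and because V.E is the stricter rule, following it inflates nothing. That is a plausible account of how the conflict arose. It does not account for the sample size, which matches the header and not V.E, so the header cannot be dismissed as a mere typing error.

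A second point is that the match depends on the formula. At one-sided 5% the total is 290, 342, 342, or 390 if the null variance is taken at 95% and 87.5%. This stands: the one-sided origin of 342 is a strong inference from two exact matches, not a documented fact. Judged on power instead of sample size, the unpooled formula at one-sided 2.5% comes close to the stated target, with 88.9% at 342 clients and a requirement of 356, about 4% more.

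Third, the plan expects to pool urban and rural sites. With about 442 clients, power at one-sided 2.5% is above 90% by every method in the table. The shortfall therefore applies if the analysis falls back on the urban sites alone, which SAP VIII describes as the powered set.

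Fourth, the disputed interval is for an odds ratio while the margin was treated here as a difference in proportions, so correcting the label does not by itself complete the decision rule. That is true, but the interval level has to be settled on either scale.

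**Conclusion.** The concern holds. The SAP gives incompatible levels for its primary test: V.E and the footnote imply one-sided 0.025, and the header of the same results table implies one-sided 0.05. The permitted false-claim rate differs two-fold, and plausible results would pass one rule and fail the other.

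The 342 clients at 90% power match one-sided 5% exactly by the two formulas that reproduce the figure. Under V.E those formulas need 408 to 424 clients, and 342 clients give about 82 to 84% power (about 89% by the unpooled formula, which gives 342 at neither level).

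The power figures rest on an absolute margin of 7.5 points, 95% success in both arms, normal approximations, and no allowance for clustering by provider or clinic, as in the plan. They are not the power of the planned logit mixed model. The conflict between the stated levels depends on none of these assumptions.

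**What to change.** State one level, with its sidedness, in V.E, section VIII, the Table 1 header, the Table 1 footnote and the sample-size text, and name the sample-size formula. Either choice is open to the sponsor.

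- **If V.E stands:** write one-sided 0.025, judged on the lower limit of the two-sided 95% CI, and change the header to 95% CI. Restate power at 342 as about 82 to 84% by the formulas that reproduce that number, and at a pooled 442 as about 91 to 93%, both before clustering.
- **If the level behind the sample size was intended:** change V.E to one-sided 0.05 for the non-inferiority test and the footnote to 90% CI. Say which level applies to the other performance outcomes, since V.E covers them too and counseling shares the table.

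In both cases, say how the interval from the mixed model will be compared with the 7.5% margin. Make the change before any data by arm, even under coded labels, reach the analysis team.

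The cost is SAP wording and, if V.E stands, a less favourable stated power. No extra clients are needed.

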## **II. Objectives and Outcomes**

The overall goal of the trial is to provide high-level evidence that lay or community health workers can safely and effectively screen and initiate women who choose to use injectable contraceptives. The primary objective is:

To assess whether the community health worker cadre, Lady Health Workers (LHWs) in Pakistan can screen and initiate women on intramuscular and subcutaneous Depo Provera injections as safely and effectively as their clinically-trained counterparts, Lady Health Visitors (LHVs).

Although LHWs are already allowed to provide follow-up doses in the community, this RCT will focus on the comparison of safety and effectiveness of screening, counseling and first-time administration of DMPA IM and SP. Rather than focusing on determining whether services are better provided by one of the two health worker cadres, we want to determine if LHWs can perform just as well as the more experienced LHVs. Therefore, the trial will be powered specifically to detect non-inferiority (i.e., no difference) within a tolerance margin in the performance of LHWs compared to LHVs with regard to screening--the procedure that determines a woman's eligibility to receive DMPA. We consider the assessment of the screening for DMPA use as the primary outcome of interest for addressing the primary objective. However, in addition to screening, metrics for counseling and administration of DMPA will constitute the endpoints for the primary objective described below:

- Proportion of Lady Health Workers and Lady Health Visitors that appropriately screen women for DMPA use;
- Proportion of Lady Health Worker and Lady Health Visitor clients that report discussion with their respective providers on side effects, danger signs, advantages and disadvantages of DMPA use;
- Proportion of Lady Health Workers and Lady Health Visitors that demonstrate appropriate injection technique
- Proportion of Lady Health Workers and Lady Health Visitors that report needle stick injuries;
- Proportion of Lady Health Workers that properly maintains a client (re)injection log.

Details on analysis of these endpoints will be provided in a separate data analysis plan.

The secondary objective is:

To assess whether DMPA clients of Lady Health Workers and Lady Health Visitors are equally satisfied with their respective providers and the family planning services they provide.

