### Data analysis

We plan to compare a series of indicators of the performance of LHWs compared to LHV in the provision of injectable contraception services. Our primary outcome is related to the screening process. We will test the non-inferiority hypothesis that LHWs can screen potential DMPA clients for method initiation just as adequately as LHV with a non-inferiority margin of 7.5%. Given the relationship between LHWs and LHV within clinics, we plan to use a generalized mixed model using a logit link to account for the correlations of participant outcomes within providers and providers within clinics. Random effects will be included for clinics and providers within clinic. The non-inferiority test will be conducted at a 5% significance level. A similar approach will be used to compare other performance outcomes. No covariate adjustments are planned for the primary analyses. However, these may be included for exploratory analyses. If any, these will be specified in the detailed analysis plan prior to data analysis. Other comparisons between groups will be primarily descriptive to explore the differences in the provision of DMPA services by each cadre of provider. Similarly, comparisons between injection techniques will be primarily descriptive and exploratory.

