IRBNET# 1035709: A randomized controlled trial of safety and effectiveness of Depo Provera intramuscular and subcutaneous administration comparing lay Lady Health Workers with clinically-trained Lady Health Visitors in Pakistan

STATISTICAL ANALYSIS PLAN

This statistical analysis plan gives a detailed explanation of the data analysis summary included in the study protocol.

I. Study Objectives

The goal of this evaluation is to assess whether the community health worker cadre, Lady Health Workers (LHWs) in Pakistan can screen and initiate women on intramuscular (IM) and subcutaneous Depo Provera injections as safely and effectively as their clinically-trained counterparts, Lady Health Visitors (LHV). Although LHWs are already allowed to provide follow-up doses in the community, this RCT will focus on the comparison of safety and effectiveness of screening, counseling and administration of DMPA IM and the subcutaneous injection, Sayana Press® (SP).

The study's primary outcomes are:

- Proportion of Lady Health Workers and Lady Health Visitors that appropriately screen women for DMPA use;
- Proportion of Lady Health Worker and Lady Health Visitor clients that report discussion with their respective providers on side effects, danger signs, advantages and disadvantages of DMPA use;
- Proportion of Lady Health Workers and Lady Health Visitors that demonstrate appropriate injection technique
- Proportion of Lady Health Workers and Lady Health Visitors that report needle stick injuries;
- Proportion of Lady Health Workers that properly maintains a client (re)injection log.

A secondary objective is to assess whether the clients of LHWs and LHV are equally satisfied with their respective providers and the family planning services they provide.

The study's secondary outcomes are:

- Satisfaction with the method;
- Satisfaction with the services received from the provider;
- Reports of client ability to speak freely and ask questions of provider;
- Friendly and respectful behavior toward client.

II. Study Design

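### Counselling is listed as a primary outcome and shares screening's alpha and non-inferiority footnote, but has no margin, no place in a testing order and no supportive label

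*SAP*

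**What the plan says.** **Status of the outcomes.** SAP I opens its list with "The study's primary outcomes are" and names five outcomes: screening, counselling, injection technique, needle-stick injuries and log keeping. Protocol II says that, beyond screening, "metrics for counseling and administration of DMPA will constitute the endpoints for the primary objective described below". The same paragraph names screening as the outcome of main interest and bases the power on it. SAP VIII also refers to screening as the primary outcome, in the singular. SAP V.D keeps the analysts partly blinded until the screening conclusion has been reached and verified.

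**Tests.** SAP VIII (Analytical model) sets out a logit mixed model and a 7.5% margin for screening, and adds "The non-inferiority test will be conducted at a 5% significance level". It continues: "A similar approach will be used to compare appropriate counseling". Protocol IV (Data analysis) is wider: "A similar approach will be used to compare other performance outcomes". SAP Table 2 (summary of analysis approach) assigns the mixed model to screening and counselling only; the other three primary outcomes are descriptive.

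**Alpha and reporting.** SAP V.E states: "The type I error for the non-inferiority test and other performance outcomes will be set at the two-sided" 0.05 level. The first results table shell (Table 1 under Objective 1) has two rows, screening and counselling. Its column heading is a 90% interval, and one footnote covers both rows: "95% CI and p-value reported for test of non-inferiority". Objective 1 is to be answered with both odds ratios.

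**Sample size.** SAP IV: "We require a minimum of 342 DMPA clients randomized to receive care from either the LHV or an LHW", for 90% power at a 5% level, with 95% success in both cadres and a 7.5% margin. These figures are given for screening only.

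**The concern.** Counselling has primary status, the same model as screening, the same unreduced alpha and an announced non-inferiority p-value. Three things are missing:

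- a counselling margin, without which a non-inferiority p-value has no defined null hypothesis;
- a rule linking the two tests, whether a sequence, an alpha split or a requirement that both pass;
- a label saying that counselling is supportive.

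Followed as written, the plan would let a counselling result be reported as a primary-outcome non-inferiority finding even if screening had failed. It also gives no verdict on Objective 1 if screening passes and counselling fails. The trial is meant to inform provincial policy and WHO guidance on lay initiation of injectables, so what each row may support should be settled before unblinding.

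**Working it through.** **1. Which error rate does the plan use?** Inputs from SAP IV: p = 0.95 in both arms, margin 0.075, power 90%, 1:1 allocation, total 342 (171 per arm).

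Simple formula: n per arm = 2p(1−p)(z₁₋α + z₀.₉₀)² / 0.075², with 2p(1−p) = 0.095.
Continuity correction: n′ = (n/4)[1 + √(1 + 4/(0.075 n))]².

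| Level per test | n per arm, simple | Total | n′ per arm | Total | Farrington-Manning total |
|---|---|---|---|---|---|
| One-sided 5% | 144.6 | 290 | 170.3 | 342 | 342 |
| One-sided 2.5% | 177.5 | 356 | 203.3 | 408 | 424 |

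The stated 342 reproduces exactly at one-sided 5%, by two methods. The 90% interval column in Table 1 fits that level. V.E (two-sided 0.05) and the 95% footnote fit one-sided 2.5%. The sample size strongly suggests one-sided 5% but does not prove it: without continuity correction, 171 per arm gives 88.9% power at one-sided 2.5%. Both levels are carried forward.

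**2. Chance of at least one false claim.** Assume that either row may support a claim and that both cadre differences lie exactly at their margins. With bivariate normal test statistics of correlation ρ:

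P(at least one) = 1 − P(Z₁ < z₁₋α, Z₂ < z₁₋α).

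At ρ = 0 this is 1 − 0.95² = 0.0975, or 1 − 0.975² = 0.0494. The documents give no correlation, so a range is shown.

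| ρ (assumed) | One-sided 5% each | One-sided 2.5% each |
|---|---|---|
| 0 | 9.75% | 4.94% |
| 0.3 | 9.3% | 4.8% |
| 0.5 | 8.8% | 4.5% |
| 0.8 | 7.5% | 3.9% |

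Ratios to the per-test rate: 9.75/5 = 1.95 down to 7.5/5 = 1.5; 4.94/2.5 = 1.98 down to 3.9/2.5 = 1.56.

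**3. If both rows had to pass.** The chance of a false double pass, with both nulls at the margin, is 2α − P(at least one). At one-sided 5% and ρ = 0.5 this is 10% − 8.8% = 1.2%. There would then be no inflation.

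**4. Screening passes, counselling fails.** Assume equal cadres, 171 per arm, no clustering, ρ = 0.5, and the 7.5% margin borrowed for counselling. Each statistic has mean 0.075/√(2p(1−p)/171). For screening at 95% this is 0.075/√(0.095/171) = 3.18. The counselling rate is an assumption, because the documents give none.

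| Counselling rate (assumed) | One-sided 5% | One-sided 2.5% |
|---|---|---|
| 95% | 5% | 7% |
| 90% | 21% | 28% |
| 80% | 41% | 49% |

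**5. After the fix.** In a fixed sequence, counselling can be claimed only after screening has passed, so the chance of any false claim is at most the per-test α: 5%, or 2.5% on the literal V.E reading.

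**The case against.** The strongest reply is that the plan already ranks its outcomes. Screening is singled out in Protocol II and SAP VIII, only screening has a margin and power, and SAP V.D settles it before full unblinding. This stands: the error rate of the screening claim is intact, and a reader who inferred that the outcomes have no ranking at all would be wrong. But neither naming an outcome nor the order of unblinding says what a counselling result may support if screening fails.

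A second reply is that a counselling non-inferiority test is only implied. V.E refers to one non-inferiority test and separately to other outcomes, and the counselling sentence speaks only of comparing. That is fair, and the Table 1 shell is inconsistent about its own interval level. Even so, its footnote does not exempt the counselling row, so as drafted the row would carry a non-inferiority p-value.

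A third reply is that the inflation needs an either-row-suffices rule that no document states. This is also correct, so the figures are conditional. An all-must-pass rule is equally absent.

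A reader might also take the wide Protocol sentence on other performance outcomes to mean that all the primary outcomes are tested for non-inferiority. The documents do not support that. Protocol II leaves the endpoint analyses to the separate plan, SAP VIII narrows the sentence to counselling, and SAP Table 2 makes the remaining three descriptive.

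**Conclusion.** The point holds as a gap in the testing rules around counselling; the screening test itself is unaffected. If either row may support a claim, the chance of at least one false claim is 1.5 to about 2 times the per-test rate for correlations of 0.8 to 0. In absolute terms this is 7.5% to 9.75% at one-sided 5%, or 3.9% to 4.9% against 2.5% under V.E as written.

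A reader might shorten this to an error rate of about 9% where 5% was promised. The documents do not support that without conditions: it needs one-sided 5% per test and the either-row reading, and on the literal V.E wording the total stays below 5%.

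Nor can a split result be called likely. On the assumptions above it ranges from 5% to 49%, driven mainly by an unknown counselling rate, and is 5% to 7% if counselling succeeds as often as the 95% assumed for screening. What is certain is that the plan has no verdict for it.

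**What to change.** In SAP V.E, SAP VIII and the Table 1 footnote:

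- Test in fixed sequence: screening first at the full alpha, then counselling for non-inferiority only if screening passes and only against a counselling margin fixed before unblinding.
- If no counselling margin is set, take counselling out of the non-inferiority footnote and report it as supportive: a risk difference with its interval and no non-inferiority p-value.
- State that a pass on screening alone supports a claim about screening only.
- State the sidedness of alpha once and match the interval level in the Table 1 column and footnote to it.

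Align the corresponding sentence in Protocol IV (Data analysis) with the SAP.

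The cost is SAP wording, one table footnote and one protocol sentence. No more clients are needed and screening loses no power. The downside is that counselling non-inferiority cannot be claimed if screening fails.
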